4. GENERAL ISSUES FOR DATA ANALYSIS

4.1. Descriptive Statistics

Descriptive statistics pertinent to pharmacokinetic analyses are described in Section 10. For all other analyses, continuous variables will be summarized using the number [n] of non-missing values, the mean, standard deviation (SD), median, minimum, maximum and other descriptive statistics, as relevant. Categorical data will be summarized using the number and percentage of subjects with a specific level of the variable. Measures of central tendency and dispersion will be reported to one decimal place greater than the original data; the minimum, maximum, and percentiles other than the median will be reported to the same number of decimal places as the original data. Proportions will be presented to three decimal places and percentages to one decimal place.

4.2. Specification of Baseline Values

The baseline value for any measurement is the last value prior to injection of study drug.

4.3. Handling of Withdrawals and Missing Data

4.3.1. Discontinuation and Missing Data

Subjects who are discontinued from the study after being randomized will not be replaced. All available data up to the time of discontinuation will be included in relevant analyses. Except as noted in Section 4.3.2, missing data will not be estimated or imputed.

4.3.2. Imputed Data

Missing MPA concentrations at key time points (e.g., end-times of partial AUCs) and MPA concentrations that fall below the lower limit of quantification (LLOQ) will be imputed using methods specified in Section 10. Other laboratory measurements that fall below an applicable LLOQ will be imputed as half the LLOQ when summarizing continuous variables. If required to interpret safety, incomplete adverse event onset, resolution, or concomitant medication use dates may be imputed as follows:

- If the month of adverse event onset or initiation of medication use is known but the day is missing, then the onset/initiation date may be imputed as the first day of the month.
- If the month of adverse event resolution or medication use stop-date is known but the day is missing, then the resolution/stop data may be imputed as the last day of the month.

Other imputation rules may be required on a case-by-case basis, as determined by the Coordinating Investigator or delegated staff member. Imputation decisions will be documented in the CSR as occurring after unblinding, as applicable.

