5.2. Safety Assessments

5.2.1. Definition of an Adverse Event

An adverse event is any untoward medical occurrence in a subject administered a pharmaceutical product, regardless of whether it has a causal relationship with the treatment.

In this study, any adverse event occurring after the clinical study subject has signed the ICF through the end of the follow-up period should be recorded and reported as an adverse event. An adverse event occurring during or after study injection is referred to as a treatment emergent adverse event

A new condition or the worsening of a pre-existing condition will be considered an adverse event. Stable chronic conditions (such as arthritis) that are present before study entry and do not worsen during this study will not be considered adverse events.

Accordingly, an adverse event can include any of the following:

- intercurrent illnesses
- physical injuries
- events possibly related to concomitant medication
- significant worsening (change in nature, severity, or frequency) of pre-existing conditions (Note: A condition recorded as pre-existing that is intermittently symptomatic [eg, headache] and that occurs during this study should be recorded as an adverse event.)
- drug interactions
- events occurring during diagnostic procedures
- laboratory or diagnostic test abnormalities, that result in the withdrawal of the subject from the study, are associated with clinical signs and symptoms or a serious adverse event, or require medical treatment or further diagnostic work-up, or are considered by the investigator to be clinically significant (Note: Abnormal laboratory test results at the screening visit that preclude a subject from entering the study or receiving study treatment are not considered adverse events.)
- all events of possible drug induced liver injury (Section [5.1.6](#))
- any physical examination, vital signs measurement, electrocardiogram, or other safety assessment finding that is judged by the investigator as a clinically significant change (worsening) compared with a baseline value will be considered an adverse event

- For the purpose of this study, irregular vaginal bleeding will not be considered an adverse event unless it requires medical intervention or meets the definition of “serious adverse event” (See Section 5.2.5).

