9.4.1. Handling Withdrawals and Missing Data

Incomplete adverse event onset or concomitant medication use dates may also be imputed or adjudicated to assess safety or when censoring subjects from analyses due to prohibited medication use.

No other missing data will be imputed unless specified in the detailed statistical analysis plan.

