11.4. Data Quality Control

The investigator is responsible for the accuracy, quality, completeness, and internal consistency of the data from this study. Data handling, including data quality control, will comply with international regulatory guidelines, including International Council for Harmonisation (ICH) GCP guidelines. Data management and control processes specific to this study, along with all steps and actions taken regarding data management and data quality control, will be described in a data management plan.

Data will be verified by the study monitor using the data source, and reviewed by Data Management using both automated logical checks and manual review. Data identified as erroneous, or data that are missing, will be referred to the investigational center for resolution through data queries. Any necessary changes will be made in the clinical database, and data review and validation procedures will be repeated as needed.

Case report forms will be processed and reviewed for completeness, consistency, and the presence of mandatory values. Applicable terms will be coded according to the coding conventions for this study. Logical checks will be implemented to ensure data quality and accuracy. Any necessary changes will be made in the clinical database, and data review and validation procedures will be repeated as needed. Data from external sources will be compared with the information available in the CDMS. Discrepancies found will be queried.

At the conclusion of the study, the CDMS and all other study data will be locked to further additions or corrections. Locking the study data represents the acknowledgement that all data have been captured and confirmed as accurate. All data collected will be approved by the investigator at the investigational center.

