4.4. Study Days and Visits

For purposes of analysis, the number of days post-injection on which an event occurs or an outcome is assessed will be calculated as the date of the event or outcome, minus the date of treatment initiation; a negative day indicates an event prior to study drug administration. When appropriate, fractions of study days will be computed based on the time (in hours and minutes) of a subject's injection and the time of her event or outcome assessment.

Although actual MPA sampling times will be used in applicable pharmacokinetics analyses (e.g., when computing AUC values), sampling times will be assigned to visit windows when reporting by-visit summaries of MPA concentrations (e.g., C_{182}). In order to maximize available data, the window periods used in these by-visit summaries may be wider than the target visit windows specified in the protocol (see [Table 2](#)).

Table 2. Pharmacokinetic data visit windows

Days since Treatment Initiation	Protocol Target	Visit Window	Visit-specific Analyses
1, 2	± 1 hour	+/ - 3 hours	
3, 5, 7	± 3 hours	+/ - 6 hours	
10, 12, 14, 18	± 24 hours	+/ - 24 hours	
21 and after (except days 91 and 182)	± 48 hours	+/ - 168 hours	
91, 182	± 48 hours	-84 / +168 hours	

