8. SAFETY ANALYSIS

8.1. General

An adverse event with onset during or after injection of study drug, or a worsening of an existing condition during or after injection, is considered a treatment emergent adverse event (TEAE); only TEAEs will be included in the safety analysis. All safety and local tolerability endpoints will be summarized for the Safety Analysis Set.

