8.3. Adverse Events

A summary table of TEAEs will include numbers of events, and numbers and percentages of subjects, experiencing: any TEAEs; serious TEAEs; related TEAEs; TEAEs by severity; TEAEs leading to study discontinuation; and TEAEs leading to death. Treatment-group differences in the percentages of subjects experiencing each TEAE category will be explored using descriptive Fisher's Exact tests. The summary table will be repeated when restricted to TEAEs with onset on or before week 52 (the end of routine follow-up).

TEAEs will be further grouped by System Organ Class (SOC) and preferred term using MedDRA™ (v23.0 or higher). Results will be displayed in order of decreasing frequency, both across SOCs and within each SOC term, by treatment group. TEAEs will also be tabulated by severity (mild, moderate, severe) and relationship to study drug, by SOC and preferred term. TEAEs (preferred term) which occur in at least 10% of subjects will be summarized separately.

Listings of TEAEs will include verbatim event description, SOC and preferred term, duration, relatedness, seriousness, severity, outcome, whether onset was during the first 52 weeks of follow-up, and whether the subject withdrew from the study as a result of the event. Information on any deaths will be described in subject narratives included in the CSR.

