12. CHANGES TO PLANNED ANALYSES

12.1. Changed from V1.0 of the SAP

The following cumulative changes were made from Version 1.0 of the SAP, prior to unblinding:

Version 2.0 (May 18, 2021)

- Section 1.2.2: Safety and local tolerability measures/parameters updated to be consistent with changes made in Protocol Amendment 02.
- Section 2.1: revised to reflect updates to assessment timepoints in Table 1 of the protocol. Specifically, addition of collection of P specimens and mood evaluation on Day 0; specimens for E2 collected on Day 0 and weeks 48, 49, 50, 51 and 52; and clarifying which visits E2 specimens will be collected if MPA or P samples are taken (starting on Day 28).
- Section 10.7: [REDACTED].

Version 3.0 (April 12, 2022)

Version 3.0 of the SAP was created to document that the above changes took place.

Version 4.0 (June 29, 2022)

Version 4.0 of the SAP clarified computation methods for apparent half-life and time above 0.2 ng/mL. The imputation of partial AE and concomitant medication start and stop dates using previous visit dates was removed as reporting date for these events was not collected. Changes to planned analyses were documented and approved prior to unblinding.

Version 5.0 (February 15, 2023)

Version 5.0 of the SAP expanded the analysis visit windows in Table 2 after blinded review of samples excluded for being out of window. These changes were not implemented for the interim analysis but were documented and approved prior to unblinding. In section 8.5, the definition of ovulation in month 12 was added as well as a definition of which subjects would be included in the denominator for the percentage calculations.

Certificate Of Completion

Envelope Id: 16B2332D2490446EBC283C9E93E0087A

Status: Completed

Subject: TV46046-10159 SAP V5.0.doc

CF02:

Project Code/Charge Code: FP0205.C01.004.004.001

Source Envelope:

Document Pages: 26

Signatures: 2

Envelope Originator:

Certificate Pages: 5

Initials: 0

[REDACTED]

AutoNav: Enabled

[REDACTED]

EnvelopeD Stamping: Enabled

[REDACTED]

Time Zone: (UTC-05:00) Eastern Time (US & Canada)

[REDACTED]

IP Address: [REDACTED]

Record Tracking

Status: Original

Holder: [REDACTED]

Location: DocuSign

2/15/2023 10:56:37 AM

Signer Events**Signature****Timestamp**

Family Health International Inc - Part 11

Security Level: Email, Account Authentication
(Required)

[REDACTED]

Sent: 2/15/2023 10:58:30 AM

[REDACTED]

Viewed: 2/17/2023 9:32:59 AM

[REDACTED]

Signed: 2/17/2023 9:34:03 AM

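### The SAP's first-of-the-month rule for partial AE onset dates has no floor at the injection date, so if the TEAE flag uses the imputed date, a post-injection event in the injection month is classed as pre-treatment

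*SAP*

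**What the plan says.** - **The date rule.** SAP 4.3.2 covers incomplete dates where this is needed to interpret safety. For a known month, if "the day is missing, then the onset/initiation date may be imputed as the first day of the month". The same section allows other rules case by case, without giving their content, and foresees that some imputation decisions may follow unblinding.
- **Study day.** SAP 4.4 subtracts the treatment date from the event date and adds that "a negative day indicates an event prior to study drug administration".
- **What is analysed.** SAP 8.1 defines a TEAE by onset or worsening during or after injection and states that "only TEAEs will be included in the safety analysis". The only AE listings that SAP 8.3 describes are of the same kind: "Listings of TEAEs will include verbatim event description".
- **What is collected.** Under Protocol 5.2.1, sites record "any adverse event occurring after the clinical study subject has signed the ICF", so real pre-injection events are in the database. SAP 12.1, cited here only for what was collected, notes that "reporting date for these events was not collected".
- **Safeguards.** Protocol 9.4.1 lets incomplete onset dates be "imputed or adjudicated to assess safety". Protocol 5.2.2 requires onset dates to be recorded. Protocol 11.4 says of "data that are missing, will be referred to the investigational center for resolution through data queries", alongside automated logical checks and manual review.

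**The concern.** The first of the month is the earliest date a partial onset could have. For most months that does no harm to TEAE status. In the month of injection it places the event before treatment unless the injection was on the 1st. Enrollment is tied to the menstrual cycle (Protocol 3.4.2), not to the calendar, so few injections should fall on the 1st.

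Within the injection month the error can go only one way: it can remove a treatment-emergent event and can never add one. The wrong date need not look wrong, because AEs are recorded from consent. The analysis data hold no reporting date to correct it, so a site query or a resolution date would be needed. At stake are counts in the safety tables of a study that compares safety across doses as a secondary objective, with about 15 women per arm.

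**Working it through.** The documents give no figure on this point, so there is none to reproduce.

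**1. What the rule does to one event.** Study day = imputed onset − injection date. With injection on day *d* of a month and onset recorded in that month, study day = 1 − *d*. Example: injection 15 March, onset recorded as March, gives 1 March − 15 March = Day −14. For *d* = 1 the result is Day 0 and nothing is lost; for *d* = 2 it is Day −1; for *d* = 28 it is Day −27.

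**2. How often the date is wrong once the rule is used.** Assume injection dates spread evenly over a 365-day year.
- Injection dates giving a negative day: 365 − 12 = 353 of 365 (96.7%).
- Pairs of injection date and same-month onset on or after it: 7 × 496 + 4 × 465 + 406 = 5,738.
- Pairs with injection on the 1st: 365. Pairs misdated: 5,738 − 365 = 5,373 (93.6%).
- With the imputed date floored at injection: 0 misdated.

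The 93.6% describes date combinations with the day missing. It is not a rate of lost events.

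**3. Exposed time.** Mean exposed days per subject, including the injection day: 5,373 / 365 = 14.7. Excluding it: (5,373 − 353) / 365 = 13.8. The maximum is 29 days after injection (injection on the 2nd of a 31-day month).

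**4. Events in that time.** Protocol 1.2.2.2 reports 51 AEs in 12 subjects in the earlier TV-46046 study, 80.4% of them (41) within 7.5 months (about 228 days), with injection site reactions (ISRs) in 9 subjects. ISRs are tabulated separately in SAP 8.4, so remove one for each of those 9 and assume all were early: 41 − 9 = 32. Assuming a constant rate:

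32 / (12 × 228) = 0.0117 per subject-day

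0.0117 × 13.8 to 14.7 days × 60 subjects = 9.7 to 10.3 events

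**5. Expected loss.** Loss = 10.3 × partial-date rate × (1 − share resolved by query), with the rule always applied to what remains. The chance of at least one is 1 − exp(−loss). The partial-date rate and query success are assumptions; the documents give neither.

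| Partial-date rate | 0% resolved | 50% resolved | 90% resolved |
|---|---|---|---|
| 1% | 0.10 (10%) | 0.05 (5%) | 0.01 (1%) |
| 5% | 0.52 (40%) | 0.26 (23%) | 0.05 (5%) |
| 10% | 1.03 (64%) | 0.52 (40%) | 0.10 (10%) |

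In the top case the chance of two or more is 1 − exp(−1.03) × (1 + 1.03) = 27.5%, so the table does not cap the loss at one event.

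**6. Effect on a table row.** One subject is 1/15 = 6.7 percentage points of an arm, but the row moves only if the lost event was her sole event in it. For the any-TEAE row, with her other AEs taken as Poisson, that chance is exp(−51/12) = 1.4% or, without the 9 ISRs, exp(−42/12) = 3.0%. For a preferred-term row, a sole event is plausible.

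**7. How easily sites could date these events.** Protocol Table 1 has visits on Days 0, 1, 2, 3, 5, 7, 10, 12, 14, 18, 21 and 28, with a longest gap of 7 days. About 95% of exposed days fall on a visit day or within 3 days before one. However, AEs are not solicited at laboratory visits; after Day 0, the only solicited visit in the first month is Day 7.

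**The case against.** The strongest reply is that the loss needs a chain of conditions: a partial date, a query that fails, a decision to impute, no adjudication or case-by-case override, and a flag derived mechanically from the imputed date. The last matters most, because the SAP never says how TEAE status is set when the day is missing. All of this stands, and the point is conditional for that reason. But discretion is not a rule: neither the case-by-case sentence nor Protocol 9.4.1 has content, and a known-month, missing-day onset already has a written rule.

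A related event dated before injection would also look contradictory, since relatedness weighs timing from administration (Protocol 5.2.4), and logical checks could flag it. This stands for related events and protects unrelated ones less.

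Another reply is that the event may still be visible. Protocol 9.6 speaks of AE listings without limiting them to TEAEs, and the mock listings sit in a separate document. So the supported statement is that the event leaves the TEAE tables and TEAE listings, not that it disappears from all reporting. Protocol 9.6 also lists serious events and events leading to withdrawal separately.

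The event rate comes from 12 subjects at 120 mg only. This protocol does not count most irregular bleeding as an AE, so the rate may not transfer. That stands and is one reason the figures are only illustrative.

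**Conclusion.** The point holds, conditionally, and is minor. Applied as written in the injection month, with the flag taken from the imputed date, the rule misclassifies every post-injection event unless injection was on the 1st. The practical loss is probably small: an expected 0.01 to 1.0 non-ISR event in 60 subjects across the assumed ranges. This rests on evenly spread injection dates, a constant event rate borrowed from the earlier study, and assumed partial-date and query-success rates. Mainly non-serious events other than ISRs are exposed.

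A reader might infer that the SAP drops most early AEs, or that it tilts the safety comparison between doses. The documents support neither. The 93.6% figure applies only to onsets whose day is missing, and all four arms face the same rule. The pharmacokinetic endpoints do not depend on it. The case for a change is that a stated rule can give a wrong answer in one direction and is easily corrected, not that the effect is large.

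**What to change.** In SAP 4.3.2, for AE onset only, add:

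> If the known onset month and year are those of injection, impute the injection date and treat the event as treatment-emergent, unless available data (e.g., a resolution date before injection) show onset before injection; otherwise impute the first of the month.

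This also settles how the TEAE flag is set in this case. Leave the medication start-date rule unchanged: a floor there could take true prior use out of the 30-day pre-treatment summary in SAP 8.11.

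The cost is one sentence and about one line of code. The downside is that an occasional pre-injection AE with a partial date will be counted as a TEAE, which is the conservative direction for a safety table.

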4.4. Study Days and Visits

For purposes of analysis, the number of days post-injection on which an event occurs or an outcome is assessed will be calculated as the date of the event or outcome, minus the date of treatment initiation; a negative day indicates an event prior to study drug administration. When appropriate, fractions of study days will be computed based on the time (in hours and minutes) of a subject's injection and the time of her event or outcome assessment.

Although actual MPA sampling times will be used in applicable pharmacokinetics analyses (e.g., when computing AUC values), sampling times will be assigned to visit windows when reporting by-visit summaries of MPA concentrations (e.g., C_{182}). In order to maximize available data, the window periods used in these by-visit summaries may be wider than the target visit windows specified in the protocol (see [Table 2](#)).

Table 2. Pharmacokinetic data visit windows

Days since Treatment Initiation	Protocol Target	Visit Window	Visit-specific Analyses
1, 2	± 1 hour	+/ - 3 hours	
3, 5, 7	± 3 hours	+/ - 6 hours	
10, 12, 14, 18	± 24 hours	+/ - 24 hours	
21 and after (except days 91 and 182)	± 48 hours	+/ - 168 hours	
91, 182	± 48 hours	-84 / +168 hours	

5. STUDY POPULATION

5.1. General

This study will recruit healthy subjects to eliminate confounding factors (comorbidities, comedications) with potential impact on study outcome. Since TV-46046 is a hormonal contraceptive, only women will be enrolled in the study. Since the contraceptive dose and duration action of TV-46046 is unknown, we will enroll women who are not pregnant, not wanting to become pregnant in the next 24 months, and who are at low risk of pregnancy because they are sterilized, in exclusively same-sex partnership, abstinent, in monogamous relationship with vasectomized partner, using non-hormonal IUD, consistent use of condoms or other barrier methods of contraception. Enrolled women will be 18 to 45 years of age and with body mass index (BMI) 18 to 35 kg/m² (inclusive).

5.2. Subject Disposition

Summaries of subject disposition will include the numbers and percentages of screened subjects who are enrolled, randomized, and contribute to the Randomized, Safety and Pharmacokinetic Analysis Sets; reasons for exclusion from analysis sets; women-years (WY) of follow-up contributed (for Randomized and Safety analysis sets) and WY of MPA testing contributed (for Pharmacokinetic analysis set); and the numbers and percentages of subjects who complete the study, discontinue early (overall and by reason), or are lost to follow-up. Disposition will be summarized by treatment group, investigational site and overall.

5.3. Demographic and Baseline Characteristics

Summary statistics appropriate for the measurement scale will be used to describe baseline data. Continuous variables may also be described using categorical levels based on previous experience with similar studies. Baseline data will be presented for the Safety Analysis Set and the Pharmacokinetic Analysis Set (the later only if any subjects are excluded from the Safety Set). Summaries will be provided by treatment group within each investigational center and pooled across centers and treatment groups. No statistical tests will be performed to compare baseline characteristics between treatment groups. [REDACTED]

[REDACTED]

[REDACTED]

[REDACTED]

